1.0 GOALS AND OBJECTIVES

1.1 Hypothesis:

In pre-adolescents, adolescents, and young adults (AYA) diagnosed with NCI/Rome High-Risk B-precursor acute lymphoblastic leukemia (HR-ALL), reducing gains in adiposity (i.e. fat mass) will improve leukemia sensitivity to induction chemotherapy, reduce post-induction minimal residual disease (MRD), reduce fatigue and obesity-associated toxicities, and improve quality of life.

1.2 Primary aim:

In AYA patients newly diagnosed with HR-ALL, to quantify the impact of a personalized dietary and activity intervention to mitigate chemotherapy-induced body fat gain throughout the critical first month of treatment ("induction").

1.3 Secondary aims:

In AYA subjects newly diagnosed with HR-ALL:

1. To compare the rate of leukemia "positive" minimal residual disease (MRD) in the bone marrow at end of induction ($\geq 0.01\%$ mononuclear cells) in those who received the intervention as compared to a historical controls.
2. To assess adherence to, and feasibility of, implementing a personalized and comprehensive dietary and exercise intervention during the first month of intensive chemotherapy

1.4. Exploratory aims:

In AYA subjects newly diagnosed with HR-ALL:

1. To evaluate persistence or extinguishing of this effect over months of continued dose-intensive pre-Maintenance phases of chemotherapy
2. To characterize the direct impact as compared to baseline of the intervention on self- and family- reported quality of life (QOL) outcomes including fatigue, mood, social interaction, and cognitive impairment reported via the PedsQL questionnaire and Child and Adolescent Scale of Participation (CASP) following the induction phase and serially during dose-intensive phases of chemotherapy.
3. To quantify the effect of adiposity on the activity of leukemogenic JAK2/STAT3, PIK3K/AKT/mTOR, MAPK/ERK, and other signaling pathways in leukemia cells as determined by kinase phosphorylation.
4. To quantify the effect of adiposity and of the intervention on the metabolic activity of leukemia blasts and of adipocytes as assessed by IGF-1, other obesity-associated cytokine signaling pathways, adiponectin, leptin, free fatty acid synthesis and metabolism, and levels oxidative stress.

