2.5 QUALITY OF LIFE DURING ALL THERAPY

As the treatment for ALL has become more successful, the assessment and improvement of patient QOL are becoming the focus for new studies and treatment modalities. To date, multiple assessment tools

have been developed to assess QOL in the pediatric cancer population. One such tool, the Pediatric Quality of Life Inventory (PedsQL), in conjunction with the PedsQL 3.0 Fatigue Module, has been shown to be particularly effective in assessing physical, emotional and social functioning, fatigue, pain, nausea, anxiety and cognitive problems among others (25).

Using this assessment tool, it has been shown that children actively undergoing chemotherapy have a lower QOL than healthy children (26) or even those 1 year removed from chemotherapy (27). Additionally, researchers have measured the changes in patient QOL over the course of ALL therapy. In patients with SR-ALL or HR-ALL, nausea, procedural and treatment anxiety and worry were worse during induction compared to maintenance therapy (28). Another similar study demonstrated a lower health-related QOL in patients in induction therapy compared to all other phases of treatment (29).

Little research has been performed to analyze the effect of physical activity on QOL in ALL patients undergoing chemotherapy. One randomized trial demonstrated improved QOL in pediatric cancer patients, including those with ALL, who participated in physical activity sessions during hospitalization (30). In adolescent survivors of ALL, leisure-time physical activity was also associated with improved QOL (31). Greater research is needed to better understand the ability of physical activity, and dietary intervention, to improve patient QOL during and after chemotherapy.

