6.0 STUDY PLAN

6.1 SUMMARY OF STUDY PLAN

Pre-adolescent and AYA patients with newly diagnosed HR-ALL will have dietary and activity preferences assessed by a registered dietician (RD) and physical therapist (PT) at the start of induction.

Subjects will receive an individualized comprehensive dietary and physical activity plan. The RD and PT will devise a personalized dietary and activity intervention aimed at creating a minimum 10% caloric deficit each day (10% nutritional + exercise) throughout the four weeks of induction therapy. Adherence to the intervention will be assessed by the RD and PT at regular weekly intervals at routine clinic visits for chemotherapy and with home phone-calls between clinic visits. Home and hospital activity will also be recorded using a wearable electronic movement monitoring device (Fitbit ®) for all participants. A list of representative “menu” of possible activity interventions from which subjects may choose is provided as a separate Appendix. The primary efficacy of the intervention will be assessed in comparison to a recent historical control via determining the change in body fat percentage (and lean muscle) during induction as quantified by dual-energy x-ray absorptiometry (DXA). A key secondary aim will be the effectiveness of the intervention to reduce chemoresistance as evidenced by decreased prevalence of leukemia minimal residual disease (MRD) at the end of induction. MRD using multicolor flow cytometry is routinely assessed as a predictor of outcome in all patients with HR-ALL. Exploratory analyses will also examine biomarkers of the proposed mechanism including adiposity and intervention-related changes in leukemogenic signaling pathways, oxidative stress, and cellular metabolism. Parent- and subject-reported QOL assessments will consist of the PedsQL and Child and Adolescent Scale of Participation (CASP) surveys (see separate Appendix) and will be conducted pre- and post-induction and at two delayed time-points (mid-point of intensive chemotherapy [3 months from diagnosis] and at end of intensive chemotherapy phase [10 months from diagnosis] to assess the psychosocial benefits of the intervention.

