6.2.4 INTEGRATION OF INTERVENTION INTO ALL THERAPY

While induction chemotherapy for pediatric ALL is a highly morbid and overwhelming time, the study team has significant experience working both with this specific population as well as other populations with high morbidity. While lifestyle changes in general are difficult to achieve, short-term changes are generally more successful and patients and families in general are more receptive to short-term achievable goals.

In this context, the 28 day intervention proposed here is purposefully designed to naturally integrate into the four week induction phase beginning with the start of systemic chemotherapy. This phase routinely includes an initial hospitalization followed by weekly clinic visits with the treating provider for delivery of chemotherapy and evaluation of toxicity. The study intervention and assessments are therefore formulated around this routine clinical schedule.

Subjects will be enrolled surrounding the time of initial diagnosis within 24 hours of starting systemic chemotherapy. Children are routinely hospitalized for a minimum of four days from the start of systemic chemotherapy. During this time, they will have their baseline DXA scan (within 96 hours from start of systemic chemotherapy), the initial PT and RD assessments, and start with the supervised activity intervention and diet intervention. Bedside nursing will be available to provide reinforcement during that time. Following anticipated discharge, the subjects will be assessed at each weekly clinic visit to have their diet and activity interventions monitored and adjusted as needed and also to receive

education/motivation from the psychosocial team. At the final clinic visit at the end of induction, subjects will receive the post-intervention assessments along with additional motivation/education. Subjects will then continue on chemotherapy per routine care with ~8-9 additional months of intensive chemotherapy; subjects will receive PT, RD, and QOL assessments midway at the start of “interim maintenance” and again at the final time-point at the start of the low-intensity maintenance phase. These follow-up visits will help gauge whether the effect of the intervention and education extinguished or persisted during the intervening post-intervention months.

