13.4 EXPLORATORY ENDPOINTS EVALUATION

To evaluate persistence or extinguishing of this effect during continued dose-intensive phases of chemotherapy

Reported continued adherence to activity and dietary recommendations will be evaluated by the RD and PT as per last prescribed or recommended from the intervention versus actual minutes/dietary intake at the delayed time-points of start of Interim Maintenance ($\sim +3$ months) and start of Maintenance ($\sim +10$ months). Activity and dietary intake patterns will also be compared to baseline at-diagnosis levels. Similar exploratory analysis will examine the effect of age, sex, race, and/or ethnicity.

To characterize the direct impact as compared to baseline of the intervention on self- and family- reported quality of life (QOL) outcomes including fatigue, mood, social interaction, and cognitive impairment reported via the PedsQL questionnaire and Child and Adolescent Scale of Participation (CASP) following the induction phase and serially during dose-intensive phases of chemotherapy

The PedsQL questionnaire returns a QOL score between 0-100 for each patient at each time-point. The CASP is scored as a percentage and then normalized to a 100 point score. Differences during therapy will be compared using a two-sided, paired t-test during induction (the intervention) and using repeated measures analysis for all four time-points.

To quantify the effect of adiposity at diagnosis on the activity of leukemogenic JAK2/STAT3, PIK3K/AKT/mTOR, MAPK/ERK, and other signaling pathways in leukemia cells as determined by kinase phosphorylation

Differences in levels of expression of the pathways will be analyzed according to body fat percentage (adiposity) using a two-sided, two-sample t-test for the different pathways as well visually for overall trends in related pathways.

To quantify the effect of adiposity and of the intervention on the metabolic activity of leukemia blasts and of adipocytes as assessed by IGF-1, other obesity-associated cytokine signaling pathways, adiponectin, leptin, free fatty acid synthesis and metabolism, and levels oxidative stress.

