14.0 ADVERSE EVENT REPORTING REQUIREMENTS

Adverse event (AE) data collection and reporting are required as part of every clinical trial to ensure the safety of patients enrolled in the studies as well as those who will enroll in future studies using similar agents. Adverse events are reported in a prescribed manner at scheduled times during the trial.

Induction chemotherapy has many associated toxicities due to the intensity of regimen, and these will be monitored per routine care by the treatment team and/or by the appropriate research team if the subject is enrolled on a concurrent therapeutic research study.

We will not record non-targeted toxicities (those described in clinical history Section 9.1) due to the underlying leukemia or treatment regimen.

As this trial consists of behavioral interventions (diet and exercise) that are within the scope of standard of care for patients, we will ONLY collect AE's that occur *during* or *immediately following* the exercise activities. If this should occur, the AE will be reported to the local IRB and the coordinating IRB (CHLA).

For an AE that occurs as above, we will record and report using the National Cancer Institute Common Terminology Criteria for Adverse Events v4.0 (CTCAE) available for download at <http://ctep.cancer.gov>.

All reporting of adverse events must include:

- severity (grade) of the event
- duration of the event
- attribution to the study (i.e. how the event is related to the study).
- whether hospitalization was necessary (or prolonged) for subjects

Categories of attribution in order of increasing likelihood are:

- Unrelated
- Unlikely
- Possible
- Probable
- Definite

All adverse events will be labeled "unexpected" for this behavioral study intervention.

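### The exploratory quality-of-life analysis describes change during therapy in treated subjects; it cannot show the impact or benefit of the intervention that the aim promises

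*Combined protocol and SAP*

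**What the plan says.** Section 1.4, exploratory aim 2, repeated as a sub-heading in Section 13.4, reads: "To characterize the direct impact as compared to baseline of the intervention on self- and family- reported quality of life (QOL) outcomes". Section 6.1 says that the PedsQL and CASP surveys "will be conducted pre- and post-induction and at two delayed time-points", about 3 and 10 months from diagnosis, and gives their purpose as "to assess the psychosocial benefits of the intervention".

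The analysis in Section 13.4 has two parts. The first is: "Differences during therapy will be compared using a two-sided, paired t-test during induction (the intervention"). The second compares the scores "using repeated measures analysis for all four time-points". No historical, published or concurrent QOL comparator is named, and nothing is said about what a significant result may be taken to mean.

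Section 6.2.4 states that the 28-day programme is designed to integrate "into the four week induction phase beginning with the start of systemic chemotherapy".

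**The concern.** The aim and the summary make a causal promise about the intervention. The analysis measures something else: how QOL moves in subjects who all receive the intervention and, over the same weeks, induction for newly diagnosed leukaemia. The parenthesis in Section 13.4 treats induction and the intervention as the same thing, which is exactly the separation the data cannot make.

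Followed as written, the plan leads to one of three errors:
- QOL rises for other reasons and is reported as benefit.
- QOL falls because of chemotherapy and is read as harm.
- A real benefit only offsets a decline, the net change is near zero, and the benefit is missed.

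Better QOL is part of the study hypothesis in Section 1.1, so readers will look for this result even though it is exploratory.

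**Working it through.** **1. What the paired difference contains.** For each subject,

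mean change = intervention effect + background change (disease, hospitalisation, steroids, chemotherapy).

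With one treated group and complete overlap in time, only the sum can be estimated. The repeated-measures analysis has the same structure, because the later time-points differ from induction in chemotherapy phase as well as in distance from the intervention.

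**2. Is the background plausibly flat?** Section 2.5 cites a study that "demonstrated a lower health-related QOL in patients in induction therapy compared to all other phases of treatment". Section 14.0 adds: "Induction chemotherapy has many associated toxicities due to the intensity of regimen". So QOL differs between phases without any intervention. This bears directly on the later time-points. It does not give the size or direction of the change from diagnosis to Day 29, because the baseline survey (Section 9.1, Day 1) is itself at the start of induction.

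**3. How the plan treats its other endpoints.**

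| Endpoint | Section | Comparator |
|---|---|---|
| Body fat by DXA | 13.2 | 36 historical subjects |
| End-induction MRD | 13.3 | 69 historical subjects |
| Oxidative stress, fatty acid synthesis | 13.4 | paired test and historical samples |
| QOL | 13.4 | none |

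**4. Illustration of the size.** The documents state no power, SD, alpha or expected change for QOL, so there is no QOL figure to reproduce. Assumptions, none of them from the documents: two-sided alpha 0.05, complete surveys in all 36 evaluable subjects (the 36 is the Section 13.1 target), zero intervention effect, a background shift of 5 or 10 points on the 0–100 scale, and SD of change 12, 15 or 20. The noncentrality is shift/SD × √36, with 35 degrees of freedom and critical value 2.03.

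| Shift | SD | Noncentrality | Probability of significance |
|---|---|---|---|
| 5 | 12 | 2.5 | 68% |
| 5 | 15 | 2.0 | 49% |
| 5 | 20 | 1.5 | 31% |
| 10 | 12 | 5.0 | 99.8% |
| 10 | 15 | 4.0 | 97% |
| 10 | 20 | 3.0 | 83% |

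These are power figures for detecting a real change over time. With no background shift the rejection rate is 5%, as it should be.

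**5. The masked-benefit case in the protocol's own numbers.** Section 13.2 gives a historical body-fat gain of 5.5 with SD 3.3 and takes a gain of 3.0 as an example of success. Assume the SD stays at 3.3. A paired test in the 36 treated subjects would give t = 3.0 / (3.3/√36) = 3.0 / 0.55 = 5.45, a highly significant worsening. Only the comparison with 5.5 shows the benefit of 2.5 points. The QOL plan has no such comparison.

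**The case against.** The case for leaving the text alone is fair in several respects. The endpoint is exploratory, with no alpha, power, threshold or go/no-go rule attached. The aim says that the comparison is with baseline, so the pre/post design is disclosed. The sentence on the test speaks only of differences during therapy, and a paired t-test is a valid test of change from baseline. Being unable to isolate an effect is inherent in a single-arm study, and Section 13.3 looks ahead to a randomised Phase III trial. All of this stands, and it limits the point to wording and interpretation. It does not remove it: disclosing a comparison with baseline is not the same as saying that the comparison cannot support a claim of direct impact.

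Three stronger readings are tempting, and the documents do not support them.
- A reader might infer that the diagnosis-to-Day-29 change would certainly occur without the intervention, and in a known direction. Section 2.5 compares treatment phases with one another and does not address that contrast.
- A reader might take the 31% to 68% as an inflated Type I error. It is not: the null hypothesis of the paired test is no change over time, and rejecting it when QOL has shifted is correct. The error lies in the attribution.
- A reader might think that regressing QOL change on adherence and change in body fat would recover the impact. Sections 7.1 and 7.2 provide for reducing or suspending activity because of complications, and for dietary non-adherence through nausea, emesis or NPO status. Adherence is therefore partly a marker of toxicity, which plausibly also lowers QOL. Adjusting for baseline QOL and age would not remove that. Body-fat change is itself the outcome that the intervention targets.

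**Conclusion.** The point holds as a mismatch between the stated aim and what the analysis can show. Both planned QOL analyses estimate change during therapy in treated subjects; neither isolates the intervention. This follows from the design and needs no numerical assumption. The direction of any misattribution is unknown.

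The illustrative 31% to 68% for a 5-point shift (83% to 99.8% for 10 points) depends wholly on the assumed shift, SD, alpha and complete surveys. It shows only that a modest background change could readily produce a significant result. The primary and key secondary conclusions are untouched. This is a minor but worthwhile correction.

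**What to change.** Reword exploratory aim 2 in Section 1.4, its repeat in Section 13.4, and the purpose given in Section 6.1, so that all three describe change in QOL during therapy in subjects who received the intervention. In Section 13.4, remove the parenthesis that equates induction with the intervention. Add one sentence saying that the paired and repeated-measures tests will not be used to claim benefit or harm from the intervention.

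Do not offer a regression on adherence or body-fat change as a measure of impact. If it is run at all, label it hypothesis-generating and confounded by toxicity.

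The cost is a few sentences, with no new data or visits. The downside is that the QOL conclusion becomes descriptive.

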5.2 EXCLUSION CRITERIA

Subjects cannot:

- Have a diagnosis of Down syndrome (Trisomy 21) or any genetic disease associated with abnormal body composition
- Be underweight or “at risk for underweight” with moderate weight loss, defined as a starting Body Mass Index (BMI) <10th percentile for age and sex (for those >20 years of age, defined as an absolute BMI < 18.5)²
- Have pre-existing abnormal intestinal function (e.g. protein-wasting enteropathy, fat malabsorption)
- Be unable to comply with both the recommended diet and activity interventions (as determined by study or treatment team)
- Have a history of prior chemotherapy or radiation for other cancers
- Be unable to complete the necessary radiology examinations with fully interpretable data (e.g. hip replacement and metal prostheses preclude evaluation by DXA)
- Be pregnant (to be confirmed by urine or serum pregnancy test as per institutional routine care for chemotherapy and radiology exams)

¹ COG = Children's Oncology Group. CCG = Children's Cancer Group

² Per the latest definition of Center for Disease Control and Prevention, underweight is defined for those <20 years of age as a BMI <5th percentile for age and sex and an absolute BMI <18.5 in adults >20 years of age. “At-risk for underweight” is a study-specific definition outlined above.

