13.3 SECONDARY ENDPOINTS Evaluation

To compare the rate of leukemia “positive” minimal residual disease (MRD) in the bone marrow at end of induction ($\geq 0.01\%$ mononuclear cells) in those who received the intervention as compared to historical controls.

The key secondary endpoint for efficacy is whether or not the bone marrow is “positive” for MRD at the end of induction (using the COG definition of $\geq 0.01\%$ mononuclear cells). From the retrospective study at CHLA of B-precursor ALL/obesity and end-induction MRD, 69 patients in the cohort had HR-ALL over the age of 10 at diagnosis. Of these, 53% of those overweight or obese (n=30) were MRD positive at the end of induction as compared to only 26% of those lean at diagnosis (n=39). Using this cohort as the historical comparison group, for the overweight/obese subset only, this study will have approximately 80% power to detect a reduction in the MRD positive rate to approximately that of the historical lean group (i.e from 53% to 24%) based on a two-sample, one-sided test of proportions with a Type I error of 0.10 (as a commonly used “go/no go” threshold to continue to Phase III trials). For the overall cohort, again in comparison to the historical cohort (MRD+ 38%, n=26/69) using a similar two-sample, one-sided test of proportions, the study will have the ability at $\sim 80\%$ power to detect a decrease in MRD by 20%. The study will therefore provide data on the potential reduction in the MRD positive rate that can be expected in preparation for the subsequent randomized Phase III trial for efficacy. These analyses will be adjusted for risk group, age, and other factors as appropriate and also compared to external published rates for MRD positivity.

To assess adherence to, and feasibility of, implementing a personalized and comprehensive dietary and exercise intervention during the first month of intensive chemotherapy

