This endpoint will be reported as the proportion of study subjects who adhere to proposed dietary and activity interventions. A threshold of 80% of RD and PT visits (combined, RD only, PT only) completed will determine feasibility of incorporating the intervention itself into induction therapy. Adherence to each component of the intervention will be further assessed using a threshold of 75% MET-minutes prescribed/completed and 75% of dietary adherence prescribed/actual intake (overall, and to each macronutrient group). Further exploratory analysis will examine which sets of activities and dietary recommendations afforded the greatest level of adherence and any trends toward adherence by age, sex, race, and/or ethnicity.

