Exploratory analyses using similar t-tests will be performed to explore the effects of adiposity at diagnosis on adipokines, obesity-associated cytokines, oxidative stress, and measures of cellular metabolism. The effect of the intervention on oxidative stress and free fatty acid synthesis will be analyzed using paired t-tests for pre/post intervention and compared to samples from the historical cohort.

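### The between-subject tests of adiposity at diagnosis on signalling and metabolic markers are not adjusted for sex or age, so a sex or age difference in a marker could be misread as an adiposity effect

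*Combined protocol and SAP*

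**What the plan says.** Section 13.4 sets out two families of between-subject tests at diagnosis.

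- Signalling pathways (aim 3): expression differences "will be analyzed according to body fat percentage (adiposity) using a two-sided, two-sample t-test for the different pathways", supplemented by visual review of trends.
- Metabolic markers (aim 4): "Exploratory analyses using similar t-tests will be performed to explore the effects of adiposity at diagnosis on adipokines, obesity-associated cytokines, oxidative stress". Cellular metabolism is to be tested in the same way.

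Neither statement names a covariate, a stratification, a cut-point for forming the two groups, or a sex- or age-specific scale for body fat percent.

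The same section treats the intervention differently: "The effect of the intervention on oxidative stress and free fatty acid synthesis will be analyzed using paired t-tests for pre/post intervention", with a comparison to historical samples.

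Section 5.1 admits ages 10 to 21 and does not restrict sex. For BMI the protocol does use an age- and sex-specific scale: Section 5.2 excludes underweight subjects, "defined as a starting Body Mass Index (BMI) <10th percentile for age and sex", and Section 13.1 identifies lean subjects by BMI percentile.

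**The concern.** Aims 3 and 4 set out to quantify the effect of adiposity. A two-sample t-test carries no covariates, so it credits adiposity with everything that differs between the higher-fat and lower-fat groups. In a sample of both sexes spanning puberty, those groups may differ in sex and age. If a marker also differs by sex or age, the test mixes that difference with any adiposity effect.

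This is confounding, so a larger sample would not remove it. Replacing the group split with an unadjusted slope would not remove it either. At stake is which pathways are carried forward as mechanisms: a marker unrelated to fat could appear on the list because it tracks sex or age.

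**Working it through.** **Step 1: does another statement cover these tests?** Three analysis statements elsewhere mention age or sex.

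| Statement | Where | What it governs |
|---|---|---|
| "These analyses will be adjusted for risk group, age, and other factors as appropriate" | 13.3 | MRD comparisons |
| "any trends toward adherence by age, sex, race, and/or ethnicity" | 13.3 | adherence |
| "Similar exploratory analysis will examine the effect of age, sex, race, and/or ethnicity" | 13.4, first aim | persistence of activity and diet |

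None reaches the marker tests.

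**Step 2: inputs.** The plan states no power, alpha or sample size for these tests, so there is no figure to reproduce.

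- From the documents: 36 evaluable subjects (13.1); body fat at diagnosis 23.3, SD 9.1 (3.0). The activity pilot in 3.0 was 68% male, hence 32% female.
- Assumed: two-sided 5% test; groups split at the median; 32% or 50% female; female-minus-male gap D points in body fat and m within-sex SDs in the marker; no true adiposity effect.

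**Step 3: one setting by hand** (D=8, m=1, 50% female).

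- Within-sex SD of body fat = √(9.1² − 8²×0.25) = √(82.81 − 16) = 8.17.
- Females lie 4 points above the overall mean, so their share of the high-fat half is Φ(4/8.17) ≈ 0.69. In simulated samples of 36 the shares were 0.684 (high-fat half) and 0.317 (low-fat half).
- Spurious marker difference = m × (0.684 − 0.317) = 0.37 SD.
- Marker SD within a half ≈ √(1 + 0.684×0.316) = 1.10. With 18 per half, the standard error is 1.10×√(2/18) = 0.37.
- The test statistic is therefore centred near 0.37/0.37 = 1 instead of 0. The rejection probability is about P(Z > 0.96) + P(Z < −2.96) ≈ 17%. The simulation gives 16.2%.

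**Step 4: simulation** (n=36, 50% female, 10,000 runs per setting, unadjusted t-test).

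| Body fat gap D | m=0.5 | m=1.0 | m=1.5 |
|---|---|---|---|
| 0 | 5.1% | 4.8% | 5.0% |
| 4 | 5.2% | 7.4% | 9.8% |
| 8 | 8.3% | 16.2% | 25.9% |

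With m=0 the rate is also about 5% for any D, so both links are needed for any inflation.

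Over D=6 to 10 and 32% or 50% female, the median-split rates are about 6–11% (m=0.5), 10–26% (m=1.0) and 13–43% (m=1.5). An unadjusted slope at m=1.0 gives about 12–31%.

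**Step 5: with sex in the model.** The rate is about 5% in every setting (4.4% to 5.8% across the runs), for both split and slope.

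**Step 6: fewer blast samples.** With n=18 to 24 (assumed) and D=6 to 10, the split rate is about 7–19% at m=1.0 and 5–8% at m=0.5. The rate falls because the test is weaker. The expected spurious difference is essentially the same.

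Age was not simulated. The argument for it is the same in kind but has no figure.

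**The case against.** The strongest reply is that the harm is conditional and cannot be sized from the documents. They give no sex or age difference in body fat percent or in any marker. If either link is absent the test holds its 5% level, and at a 4-point body fat gap the inflation is slight (about 5% to 10%). This stands, and it limits the wording to *could*.

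Several further limits also stand.

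- n=36 is generous for the signalling tests. Section 9.1 collects peripheral blasts only at an absolute count of at least 500/µL, marrow aspirate is taken only if enough specimen remains (9.1, 9.3), and other studies have prior claim on samples (5.4). One assumed sex gap need not suit both blast phosphorylation and circulating adipokines.
- Age at diagnosis is only a proxy for puberty. Pubertal stage is not in the Section 9.1 schedule.
- The plan does not say how the two groups are formed, so a sex-specific cut-point is neither stated nor excluded.
- The aims are exploratory, with no error rate or decision rule attached.

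A reader might infer that sex and puberty differences will be reported as adiposity mechanisms, or that aims 3 and 4 fail as a whole. The documents support neither reading. The first needs gaps that they do not give. The second overlooks the paired pre/post tests, in which each subject is their own control and stable sex differences cancel.

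Exploratory status lowers the stakes but does not make a confounded contrast interpretable, and the objection identifies no text that supplies the adjustment.

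**Conclusion.** The concern holds as a minor, conditional point. The plan specifies two-sample t-tests of markers at diagnosis by body fat percent, with no stated adjustment or standardisation for sex or age, and its age and sex statements elsewhere do not extend to them.

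Under assumed sex gaps of 4 to 10 points in body fat and 0.5 to 1.5 SD in the marker, with n=36 and a median split, the false-positive rate is about 5% to 43%. The upper end needs both gaps to be large. These figures illustrate the mechanism; they do not estimate the bias in this trial.

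The reach is limited to the between-subject tests at diagnosis under exploratory aims 3 and 4. The primary body fat comparison and the secondary MRD and feasibility conclusions are untouched.

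**What to change.** In 13.4, state that the between-subject adiposity–marker analyses at diagnosis use a linear model of the marker on body fat percent, with sex and age at diagnosis as covariates. Note there that age stands in for pubertal stage, which is not collected.

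Add that where blast samples are too few to carry two covariates, the comparison will use the BMI categories of 13.1, which rest on age- and sex-specific percentiles. The paired pre/post tests need no change on this account.

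The cost is two sentences and two degrees of freedom. Age is needed for eligibility, and age and sex are both needed for the BMI percentile, so nothing new is collected.
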